## **7.8 Efficacy Analysis**

Efficacy analysis will be performed using FAS in Parts 1 and 2 separately.

### **7.8.1 Primary Efficacy Endpoint(s)**

Not applicable.

### **7.8.2 Secondary Efficacy Endpoint(s)**

Not applicable.

### **7.8.3 Exploratory Efficacy Endpoint(s)**

CCI

CCI

CCI

## 7.9 Pharmacokinetic/Pharmacodynamic Analysis

### 7.9.1 Pharmacokinetic Analysis

#### 7.9.1.1 Pharmacokinetic Concentrations

Blood samples (one 4-mL sample per scheduled time) for the measurement of plasma concentrations of TAK-935 and its metabolite M-I will be collected according to [Table 7.c](#).

**Table 7.c Collection of Plasma Samples for Measurement of TAK-935 and M-I in Plasma**

Study Part	Study Day/Visit	Scheduled Time
Part 1	Day 1	Before and 1, 3, 5 hours after morning dose
	Days 11 and 21	Before and ~1 hour after morning dose
Part 2	Days 31, 41 and 85	Before morning dose

The plasma concentration of TAK-935 and its metabolite M-I will be listed for each subject and summarized by each time point for each dose and part of the study (N, mean, SD, median, minimum, and maximum).

#### 7.9.1.2 Pharmacokinetic Parameters (Secondary Endpoints)

A population PK analysis approach will be used to determine the population estimates for TAK-935. The PK analysis will be described in a separate analysis plan, and the PK parameters for TAK-935 will be summarized in a separate population PK/PD report.

### 7.9.2 Pharmacodynamic Analysis

#### 7.9.2.1 Pharmacodynamic Concentrations

CCI

CCI

### 7.9.3 Concomitant AEDs Analysis

CCI

### 7.9.3.2 *Parameter and Analysis*

CCI

CCI

## 7.11 **Safety Analysis**

Safety analyses include AEs, clinical laboratory parameters, vital sign parameters, 12-lead ECG results, and other safety parameters. The safety analysis set will be used for all summaries of safety parameters. The safety endpoints will be presented by placebo TAK-935, and overall in Part 1, by placebo, TAK-935 received in Part 1 and overall in Part 2 of the study, and by placebo, TAK-935 received in Part 1 and overall for Part 1 and 2 combined.

### 7.11.1 **Adverse Events**

A Pre-Treatment Event (PTE) is defined as any untoward medical occurrence in a clinical investigation subject who has signed informed consent to participate in a study, but prior to administration of any study medication; it does not necessarily have to have a causal relationship with study participation.

An AE is defined as any untoward medical occurrence in a clinical investigation subject administered a drug; it does not necessarily have to have a causal relationship with this treatment. PTE and AE verbatim terms will be coded by SOC and PT using MedDRA (version 19 or later).

TEAEs for Part 1 will be defined as any sign, symptom, syndrome, or new illness, regardless of relationship to study drug, that occur after the first dose of study drug received in Part 1 and up to 30 days (onset date – last date of dose + 1 ≤ 30) after the last dose of study drug in Part 1 or

early termination. AEs that occur on the same day as the first dose of study drug in Part 1 but with missing time will be considered as TEAEs for Part 1.

TEAEs for Part 2 will be defined as any sign, symptom, syndrome, or new illness, regardless of relationship to study drug, that occur after the first dose of study drug received in Part 2 and up to 30 days (onset date – last date of dose + 1 ≤ 30) after the last dose of study drug in Part 2 or early termination. AEs that occur on the same day as the first dose of study drug in Part 2 but with missing time will be considered as TEAEs for Part 2.

TEAEs for Part 1 and 2 combined will be defined as any sign, symptom, syndrome, or new illness, regardless of relationship to study drug, that occur after the first dose of study drug received in Part 1 and up to 30 days (onset date – last date of dose + 1 ≤ 30) after the last dose of study drug in Part 2 or early termination. AEs that occur on the same day as the first dose of study drug in Part 1 but with missing time will be considered as TEAEs for Part 1 and 2.

TEAEs will be presented by severity (mild, moderate, and severe). Serious TEAEs, TEAEs leading to study drug discontinuation, and TEAEs leading to death will also be summarized using SOC and PT.

When calculating the frequency and percentage of subjects who reported TEAEs, a subject will be counted only once for each SOC or PT when multiple TEAEs are coded to the same SOC or PT. For the intensity or relatedness summaries, if a subject reports multiple TEAEs coded to the same SOC or PT, the TEAE with maximum intensity or strongest relationship will be included in the summary.

AEs with missing severity will be listed as such in the AE listings, however, will be summarized as severe in summary tables. Similarly, if the relationship of an event is missing, the event will be considered as related but in listings it will be presented as missing.

In general, AEs will be tabulated at the following levels: overall summary (subjects with at least 1 AE in any dose or treatment), the MedDRA SOC, and the MedDRA PT. The tables will include the number and percentage (N[%]) of subjects. The following summary tables will be generated for each study part (Part 1 and Part 2):

- Overview of Treatment-Emergent Adverse Events
- Treatment-Emergent Adverse Events by System Organ Class and Preferred Term
- Treatment-Emergent Adverse Events by Preferred Term
- Serious Treatment-Emergent Adverse Events by System Organ Class and Preferred Term
- Most Frequent (>5% or N>2) Non-Serious Adverse Events by Preferred Term
- Most Frequent (>5% or N>2) Non-Serious Adverse Events by System Organ Class and Preferred Term
- Relationship of Treatment-Emergent Adverse Events to Study Drug by System Organ Class and Preferred Term

- Drug-Related Treatment-Emergent Adverse Events by System Organ Class and Preferred Term
- Drug-Related Treatment-Emergent Adverse Events by Preferred Term
- Severity of Treatment-Emergent Adverse Events by System Organ Class and Preferred Term
- Pretreatment Adverse Events by System Organ Class and Preferred Term

In addition, subject mappings for the TEAEs by SOC and PT will be generated.

Data listings will be provided for PTEs, TEAEs, TEAEs leading to study drug discontinuation, SAEs, and AEs that resulted in death.

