Part 2 of the study is designed to investigate the safety, tolerability, PK, and PD of TAK-935 in adult subjects with developmental and/or epileptic encephalopathies in an open-label manner. All subjects who complete the Double-Blind Treatment Period in Part 1 will have the option to continue directly into the Open-Label Treatment Period in Part 2. Because some subjects may enter Part 2 after receiving placebo and others TAK-935 up to 300 mg BID and to maintain the study blind, all subjects will start on TAK-935 200 mg BID at the start of Part 2. On Day 31 (Visit 5), subjects will return to the clinic and receive TAK-935 200 mg BID from Days 31 to 40 but may be reduced to 100 mg BID in subjects who cannot tolerate the 200 mg BID dose or demonstrate safety concerns, based on the investigator's judgment and in consultation with the subject's caregiver, when applicable. Subjects who cannot tolerate the 100 mg BID dose or demonstrate safety concerns, based on the investigator's judgment and in consultation with the subject's caregiver, will be discontinued from the study. On Day 41 (Visit 6), subjects will return to the clinic; at this visit, the investigator will review the subject's safety data and will discuss the benefit-risk with the subject or subject's legally acceptable representative before proceeding to increase the dose from 200 mg BID to 300 mg BID, and this dose level will be maintained until the Final Visit (Visit 7) for the dose de-escalation phase. Subjects' dose may be increased or decreased before Day 41 (Visit 6) based on clinical condition (ie, increasing seizures) and investigator judgment. This dose may be reduced to 200 mg BID in subjects who cannot tolerate the 300 mg BID dose or demonstrate safety concerns, as described above. Subjects for whom the dose was reduced to a lower dose level will stay on that dose level until the Final Visit (Visit 7) for the dose de-escalation phase. Three days after each dose up-titration or de-escalation, subjects will be contacted by phone to monitor study drug compliance, concomitant medication use, and AEs. Any change in dose will be documented in the subject's clinic chart and the subject's caregiver will be advised to note the same in the dosing card.

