## 7.2 Analysis Sets

The randomized set will include all subjects who were randomly assigned to planned treatment through the IVRS/IWRS.

The PK analysis set for Parts 1 and 2 will include all subjects who received at least 1 dose of study drug and have at least 1 post-dose measurable TAK-935 or M-I plasma concentration.

CCI

The full analysis set (FAS) for Parts 1 and 2 will include all subjects who were randomized, received at least 1 dose of study drug, and have at least 1 valid post-baseline value for assessment of the efficacy endpoint(s) in Part 1 or Part 2. In FAS efficacy summaries, subjects will be analyzed according to the treatment to which they were randomized.

The safety analysis set for Parts 1 and 2 will include all subjects who received at least 1 dose of study drug. In safety summaries, subjects will be analyzed according to the actual treatment they received.

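### The Part 1 TEAE window in the SAP does not stop at the first open-label dose, so events that start on open-label TAK-935 can be counted in the Part 1 placebo column

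*SAP*

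**What the plan says.** SAP 7.11.1 gives three TEAE definitions: Part 1, Part 2, and both parts combined. Part 1 covers events "that occur after the first dose of study drug received in Part 1 and up to 30 days" "after the last dose of study drug in Part 1" or early termination, with the limit written as "onset date – last date of dose + 1 ≤ 30". The Part 2 definition has the same form and opens at the first Part 2 dose. An event on the date of that dose "but with missing time will be considered as TEAEs for Part 2". Nothing in the section assigns an event that meets both definitions to one part only.

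SAP 4.4 states that "all subjects will start on TAK-935 200 mg BID at the start of Part 2", with Part 2 starting on Day 31. Protocol 9.3.4 puts the first open-label dose on the morning of that day, so there is no gap after Part 1.

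On presentation, SAP 7.11 says: "The safety endpoints will be presented by placebo TAK-935, and overall in Part 1". For Part 2 the columns are again "by placebo, TAK-935 received in Part 1 and overall in Part 2 of the study". SAP 7.2 adds: "In safety summaries, subjects will be analyzed according to the actual treatment they received". Protocol 13.1.3.1 makes TEAEs a primary endpoint in each part, asks for summaries by treatment group within each part, and leaves the TEAE definition to the SAP.

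**The concern.** A 30-day tail after the last dose suits a subject who stops treatment. For a subject who goes straight on to open-label drug, the same tail runs through the first month of Part 2. Read literally, a former placebo subject who has an event on Day 35, while taking TAK-935, is a placebo subject with a Part 1 TEAE. The same event is reported again under Part 2.

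Part 1 is the only part with a concurrent placebo column, and that column has four planned subjects. It could show events that began on active drug, including events judged drug-related. Of the 11 tables that 7.11.1 lists for each part, 8 carry the TEAE definition in their title: the overview, SOC and PT, PT alone, serious, relationship, drug-related by SOC and PT, drug-related by PT, and severity.

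**Working it through.** The plan gives no figure to reproduce here; the check applies its own inequality to its own calendar.

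**Inputs**
- Last Part 1 dose: nominal Day 30 (SAP 4.4).
- First Part 2 dose: nominal Day 31 (SAP 4.4, Protocol 9.3.4).
- Part 1 limit: onset − last dose + 1 ≤ 30 (SAP 7.11.1).
- Window for the Day 31 visit: ±2 days (Protocol Appendix A).
- Planned arms: 16 TAK-935, 4 placebo (SAP 4.4).
- Up to 6 replacements (Protocol 7.6).

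**Overlap**
- Onset ≤ last dose + 29, so with Day 30 the window ends on Day 59.
- Days 31 to 59 are 59 − 31 + 1 = 29 days, and 29/59 = 49.2% of the Part 1 window.
- On the nominal schedule these are 10 days at 200 mg BID (Days 31–40) and 19 days at 300 mg BID (Days 41–59). Dose changes in Part 2 would alter that split.
- Visit on Day 29: last Part 1 dose Day 28, window to Day 57, overlap Days 29–57 = 29 of 57 days.
- Visit on Day 33: last Part 1 dose Day 32, window to Day 61, overlap Days 33–61 = 29 of 61 days.
- Afternoon visit on Day 31, assuming the morning dose taken at home is a Part 1 dose: last Part 1 dose Day 31, window to Day 60, overlap up to 30 of 60 calendar dates.

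An onset on the changeover day but before the first open-label dose belongs to Part 1 in any case.

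**Effect on the Part 1 percentages**

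The step is 100/n for each subject whose first TEAE falls in the overlap. Replaced subjects who were dosed stay in the safety set, so n can grow.

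| Arm | Planned n | One replaced | All six replaced in that arm |
|---|---|---|---|
| Placebo | 1/4 = 25 points | 1/5 = 20 points | 1/10 = 10 points |
| TAK-935 | 1/16 = 6.25 points | 1/17 = 5.9 points | 1/22 = 4.5 points |

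With 4 placebo subjects, k affected subjects add 25k points, k = 0 to 4. The documents give no TEAE rate and no continuation rate, so k cannot be derived.

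**Do other rules remove the overlap?**
- SAP 7.2 (actual treatment) and SAP 7.11 (columns by Part 1 treatment) classify subjects. Neither moves an event from one part to the other.
- SAP 7.1.3.1, on partial AE start dates, applies the 30-day tail to subjects who do not continue and otherwise uses the first Part 2 dose as the boundary. It governs incomplete dates only.
- The missing-time rule places an event on the first Part 2 dose date in Part 2 but does not take it out of Part 1.

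**The case against.** The strongest reply is that the intended cut is already visible. The partial-date rules in SAP 7.1.3.1 use the first Part 2 dose as the boundary for subjects who continue, and Protocol 13.1.3.1 speaks of events during a part of the study. A programmer who reads the whole SAP might well apply the cut unprompted. That stands as evidence of intent, and it makes this a drafting omission rather than a deliberate choice. It does not change the rule for complete dates, because the protocol leaves the definition to 7.11.1 and 7.11.1 has no cut.

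A second reply concerns weight. The primary endpoint is worded in terms of TEAEs after TAK-935 treatment, so the placebo column is a descriptive comparator. No statistical testing is planned for TEAEs, and the listings let a reader trace each event. For the TAK-935 arm an event in the overlap still follows TAK-935 treatment, so the fault there is allocation to the wrong part and double reporting. Only former placebo subjects can have an event shown under the wrong treatment. All of this stands and limits the severity.

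Third, the 49% is a share of window days, not a bias in the TEAE percentage, and the number affected may be zero. That is correct. Both arms can gain events in the overlap, so the net effect on the difference between arms cannot be signed either.

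**Conclusion.** The concern holds. As written, the Part 1 TEAE definition takes in 29 days of open-label treatment (30 dates in the afternoon-visit case) for every subject who continues. Events starting in that time count under both parts and, for former placebo subjects, in the Part 1 placebo column. Each affected placebo subject moves that column by 25 points at the planned size, less if dosed subjects are replaced; the number affected is unknown.

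This rests on a literal reading of 7.11.1, the nominal dosing days, and continuation into Part 2 without a gap. It affects the tabulated Part 1 percentages of a primary endpoint. It loses no data, alters no test, and leaves the Part 2 and combined summaries unchanged. It should be fixed before the tables are programmed.

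**What to change.** In SAP 7.11.1, add that for subjects who enter Part 2 the Part 1 TEAE window ends at the first Part 2 dose, if that comes before the existing limit, and that events on that date with no recorded time count in Part 2 only. Keep the present window for subjects who do not enter Part 2. This brings the definition into line with the boundary already used for partial dates, and the overlap falls to zero.

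Confine the rule to adverse events. The baseline convention in SAP 7.1.1 already excludes them and should stay, since Day 31 is a scheduled laboratory and ECG assessment.

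The cost is one sentence and one programming condition. SAP 7.7 already lists the first open-label dose date. The number of continuing subjects with a Part 1 TEAE can only fall or stay the same. In tables by maximum intensity or strongest relationship a subject may move to a lower category, so a single category's count could rise. Results for subjects who do not continue do not change.

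A separate, minor point: the wording allows 30 days after the last dose, while the bracketed formula allows 29. Aligning the words to the formula changes no result; aligning the formula to the words moves the end of all three windows by one day, except where the new cap applies.

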### **7.11.2 Clinical Laboratory Evaluations**

Clinical laboratory tests will be assessed using the safety analysis set and will be evaluated and presented using International System of Units (SI) unless otherwise stated. [Table 7.f](#) shows a list of all clinical laboratory tests.

**Table 7.f Clinical Laboratory Tests**

Hematology	Serum Chemistry	Urinalysis (a)	Study Specific
RBC	ALT	pH	Plasma
WBC with differential (% and absolute)	Albumin	Specific gravity	CCI
Hemoglobin	Alpha-1-acid glycoprotein	Protein	
Hematocrit	Alkaline phosphatase	Glucose	Plasma (Concomitant AEDs)
Platelets	AST	Blood	Carbamazepine
PT/INR	Total bilirubin	Nitrite	Clobazam
aPTT	Creatinine	Microscopic Analysis: (b)	Valproic acid
	Blood urea nitrogen	RBC/high power field	Phenytoin
	Creatine kinase	WBC/high power field	Topiramate
	GGT	Epithelial cells, casts etc	Lamotrigine
	Potassium		Rufinamide
	Sodium		Zonisamide
	Glucose		Phenobarbital
	Chloride		Levetiracetam
	Bicarbonate		Lacosamide
	Calcium		10-hydroxycabazepine (metabolite of oxcarbazepine)
	Total cholesterol		Felbamate
	HDL cholesterol		
	LDL cholesterol		
	Triglycerides		
	FSH (c)		
	Estradiol (d)		

**Diagnostic Screening**

Serum	Urine (a)
HIV	Drug screen including amphetamines, barbiturates,
HBsAg and anti-HCV	benzodiazepines, cannabinoids, cocaine, opiates, alcohol, and
HCV RNA detection by qPCR (e)	cotinine
hCG (for pregnancy) (f)	hCG (for pregnancy) (f)

aPTT= activated partial thromboplastin time, FSH=follicle-stimulating hormone, GGT=γ-glutamyl transferase, HDL=high-density lipoprotein, LDL=low-density lipoprotein, PT=prothrombin time, RBC=red blood cell; WBC=white blood cell.

(a) If urine cannot be collected at the time of the Screening Visit or other Visits due to the subject's cooperation or because the subject is wearing a diaper, it is acceptable for the subject to continue in the study and the reason should be documented in the source document.

(b) Only if dipstick results are positive.

(c) For diagnostic purposes in female subjects only.

(d) In female patients only

(e) Subjects who are positive for hepatitis C Ab should return to the clinic for an unscheduled visit to provide a blood sample for HCV qPCR.

(f) Only for female subjects of childbearing potential. If urine cannot be collected at Visit 2, the reason should be documented in the source document and the results of the serum pregnancy test obtained at Visit 1 must be confirmed to be negative by the investigator prior to randomization. An additional serum hCG pregnancy test will be performed at the Final Visit.

All laboratory test parameters will be displayed in individual subject data listings in both SI units and conventional (CV) units. For test results not in SI units, the conversion to SI units will be done in derived analysis data sets using the known conversion factors. If necessary, SI units from the central laboratory may be converted to Takeda's preferred SI units in the derived dataset. All summaries and analyses will be based on the values using these preferred SI units.

Only observations within 7 days of the last dose of study drug will be included in the tables. No inferential statistics will be presented unless otherwise stated.

Descriptive statistics (N, mean, SD, median, minimum, and maximum) for the observed and change from baseline values will be presented for Parts 1 and 2 separately. Study baseline defined in Section 7.1.1 will be used for change from baseline in each part of the study. Note that character urinalysis tests will only be listed.

Laboratory Markedly Abnormal Values (MAVs), identified by the criteria defined in [Appendix A](#), will be tabulated. If a subject has a MAV for a particular laboratory test, all visits for that subject for that parameter will be listed. The number and percentage of subjects with at least 1 post-dose markedly abnormal laboratory test result will be summarized. The mapping of the subjects who meet the MAV criteria will be listed as a table. All observations, including ones at unscheduled visits, will be included in the MAV evaluation and summaries if MAV criteria are satisfied.

All clinical laboratory data will be presented in both SI and conventional units in data listings.

### 7.11.3 Vital Signs

Descriptive statistics (N, mean, SD, median, minimum, and maximum) will be used to summarize vital sign parameters at baseline, each post-baseline visit, and change from baseline to each post-baseline visit for both Parts 1 and 2. Study baseline defined in Section 7.1.1 will be used. Only observations within 7 days of the study drug will be included in the tables.

Vital sign MAVs, identified by the criteria defined in [Appendix B](#), will be tabulated. If a subject has a MAV for a particular vital signs parameter, all visits for that subject for that parameter will be listed. The number and percentage of subjects with at least 1 post-dose markedly abnormal vital signs measurement will be summarized. The mapping of the subjects who meet the MAV criteria will be listed as a table. All observations, including ones at unscheduled visits, will be included in the MAV evaluation and summaries if MAV criteria are satisfied.

All vital signs will be listed in a data listing.

### 7.11.4 12-Lead ECGs

Descriptive statistics (N, mean, SD, median, minimum, and maximum) of ECG parameters, including heart rate, PR interval, RR interval, QRS interval, QT interval, and QTc interval (Fredericia's and Bazett's corrections), will be presented for baseline, each post-baseline visit, and change from baseline to each post-baseline visit for both Parts 1 and 2. Study baseline defined in Section 7.1.1 will be used. Only the scheduled measurements will be included in the

summary. Only observations within 7 days of the study drug will be included in the tables. No inferential statistics will be presented.

ECG MAVs, identified by the criteria defined in [Appendix C](#), will be tabulated. If a subject has a MAV for a particular 12-lead ECG parameter, all visits for that subject for that parameter will be listed. The number and percentage of subjects with at least 1 post-dose markedly abnormal 12-lead ECG measurement will be summarized. The mapping of the subjects who meet the MAV criteria will be listed as a table. All observations, including ones at unscheduled visits, will be included in the MAV evaluation and summaries.

Overall ECG interpretation category (normal, abnormal not clinically significant, abnormal clinically significant, not evaluable) is collected by eCRF at baseline and at each scheduled post-baseline visit. Shifts in ECG interpretation will be presented as cross-tabulations (baseline versus each post-baseline visit) of numbers of subjects with normal, abnormal not clinically significant, and abnormal clinically significant interpretations, not evaluable, with missing, if applicable, and total categories by each treatment (placebo, TAK-935).

All ECG parameters will be listed in a data listing.

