#### **9.1.14 ECG Procedure**

A 12-lead ECG will be recorded. If the subject cannot tolerate being supine, a sitting ECG may be obtained. The investigator (or a qualified observer at the study site) will interpret the ECG using 1 of the following categories: within normal limits, abnormal but not clinically significant, or abnormal and clinically significant. The interpretation of the ECG will be recorded in the source documents and in the eCRF. The time that the ECG was performed will be recorded. The following parameters will be recorded on the eCRF from the subject's ECG trace: heart rate, RR interval, PR interval, QT interval, QRS interval with QTcF, and corrected QT interval. ECG traces recorded on thermal paper will be photocopied to avoid degradation of trace over time.

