#### 13.1.3.2 Other Safety Endpoints

Absolute values and changes from Screening/Baseline for clinical laboratory tests, vital signs, and ECGs will be summarized by treatment group for each part of the study using descriptive statistics. Clinical laboratory test, vital sign, CCI [REDACTED] and ECG results that are outside the normal ranges and potentially clinically significant will be flagged and tabulated. The number and percentage of subjects with clinical laboratory test, vital sign, weight/BMI, and ECG parameter values that meet Takeda's predefined criteria for markedly abnormal values at least once postdose will be summarized by treatment and part of the study. Physical examination findings will be listed by subject and treatment group for each part of the study.

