**Appendix B Criteria for Markedly Abnormal Vital Signs**

Parameter	Unit	Lower Criteria	Upper Criteria
Pulse	bpm	<50	>120
Systolic blood pressure	mm Hg	<85	>180
Diastolic blood pressure	mm Hg	<50	>110
Body temperature	°C	< 35.6	>37.7

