### Appendix C Criteria for Markedly Abnormal 12-Lead ECG Parameters

Parameter	Unit	Lower Criteria	Upper Criteria
Heart Rate	bpm	< 50	> 120
PR	msec	$\leq 80$	$\geq 200$
RR	msec	$\leq 600$	$\geq 1440$
QRS	msec	$\leq 80$	$\geq 180$
QT Interval	msec	$\leq 50$	$\geq 460$
QTcF Interval	msec	$\leq 50$	$\geq 500$ OR $\geq 30$ change from baseline and $\geq 450$

ELECTRONIC SIGNATURES

Signed by	Meaning of Signature	Server Date (dd-MMM-yyyy HH:mm 'UTC')
PPD	Biostatistics Approval	31-Oct-2018 13:35 UTC
	Clinical Approval	31-Oct-2018 13:51 UTC
	Biostatistics Approval	01-Nov-2018 15:55 UTC

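### Heart-rate and RR limits for a markedly abnormal ECG disagree, and the counts of markedly abnormal values do not separate new abnormalities from those present before dosing

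*SAP*

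**What the plan says.** The percentage of subjects with at least one markedly abnormal value (MAV) in laboratory tests, vital signs or ECG following TAK-935 is a secondary endpoint (SAP 5.2). Protocol 13.1.3.2 refers to the sponsor's "predefined criteria for markedly abnormal values at least once postdose will be summarized by treatment and part of the study".

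The SAP applies one counting rule in three places:
- 7.11.2: "The number and percentage of subjects with at least 1 post-dose markedly abnormal laboratory test result will be summarized".
- 7.11.3: "The number and percentage of subjects with at least 1 post-dose markedly abnormal vital signs measurement will be summarized".
- 7.11.4: "The number and percentage of subjects with at least 1 post-dose markedly abnormal 12-lead ECG measurement will be summarized".

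All three sections include unscheduled observations, list every visit of the affected parameter for a subject with a MAV, and map the subjects concerned in a table. Part 2 safety results are shown "by placebo, TAK-935 received in Part 1 and overall in Part 2 of the study" (SAP 7.11), with a further presentation for both parts combined.

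Protocol 9.1.14 records "heart rate, RR interval, PR interval, QT interval, QRS interval with QTcF, and corrected QT interval" from each trace. SAP Appendix C then gives heart rate and RR separate MAV rows: below 50 or above 120 bpm, and at most 600 or at least 1440 msec. Appendix B, "Criteria for Markedly Abnormal Vital Signs", sets pulse at below 50 or above 120 bpm. The only criterion that refers to baseline is one branch of the QTcF row in Appendix C. The only planned categorical shift table is for the overall ECG interpretation (SAP 7.11.4).

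**The concern.** Heart rate and RR measure the same thing on the same trace, so their limits should convert into each other unless a difference is intended. They do not, and the SAP gives no reason. A reader who looks at the heart-rate row, or at the pulse limits in Appendix B, would misjudge which rates put a subject into the any-ECG percentage.

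The second matter is separate. The endpoint is worded as something that follows treatment, yet a subject who was beyond a limit before dosing and stays there is counted in the same way as one who crosses it on drug. With 16 subjects planned on TAK-935 and 4 on placebo in Part 1, one or two such subjects change the percentages visibly, and four placebo subjects are too few to show the background rate reliably. The trial's primary objective is safety and no inferential safety test is planned, so the descriptive counts are the result that readers will use.

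**Working it through.** **Heart rate against RR.** Inputs: SAP Appendix C. Formula: heart rate (bpm) = 60000 / RR (msec).

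- RR 600 msec: 60000/600 = 100 bpm. The heart-rate row has 120, a gap of 20 bpm.
- RR 1440 msec: 60000/1440 = 41.7 bpm. The heart-rate row has 50, a gap of 8.3 bpm.
- In reverse, 120 bpm is 500 msec and 50 bpm is 1200 msec.

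The RR limits therefore do not reproduce the stated heart-rate limits. Applying both rows:

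| Rate (bpm) | RR (msec) | MAV by heart rate | MAV by RR |
|---|---|---|---|
| 41 | 1463.4 | yes | yes |
| 45 | 1333.3 | yes | no |
| 50 | 1200.0 | no | no |
| 99 | 606.1 | no | no |
| 100 | 600.0 | no | yes |
| 110 | 545.5 | no | yes |
| 120 | 500.0 | no | yes |
| 121 | 495.9 | yes | yes |

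RR is stricter at fast rates and looser at slow rates, so neither rounding nor a margin in one direction explains the gap. A count that accepts either row acts, for rate, as below 50 or at least 100 bpm.

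**Pre-existing abnormalities.** The entry rules were set beside the MAV limits to see whether a subject can enter already beyond a limit.

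- ALT or AST: Protocol 7.2 item 12 asks for consultation with the Medical Monitor above 2.5 × ULN and does not exclude automatically. It does exclude results that suggest a clinically significant underlying disease. The MAV limit is above 3 × ULN (SAP Appendix A).
- HDL cholesterol: a MAV below 40 or above 60 mg/dL (SAP Appendix A). Protocol 7.1 and 7.2 set no numeric entry limit for HDL.
- ECG: Protocol 7.2 item 11 lets a subject with an abnormal but not clinically significant ECG enter with sign-off.

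Such subjects can therefore enter, and if unchanged they count. One subject, not otherwise counted, adds 1/16 = 6.25 percentage points on TAK-935 or 1/4 = 25 points on placebo in Part 1.

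The documents give no baseline MAV frequency. As an illustration only, assume that a share q of subjects has a MAV at baseline, that it persists, that the drug has no effect and that subjects are independent. The expected number carried over is nq, and the chance of at least one is 1 − (1 − q)^n.

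| q | Expected of 16 | Chance of ≥1 of 16 | Expected of 4 | Chance of ≥1 of 4 |
|---|---|---|---|---|
| 5% | 0.8 | 56% | 0.2 | 19% |
| 10% | 1.6 | 81% | 0.4 | 34% |
| 25% | 4.0 | 99% | 1.0 | 68% |

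**The case against.** The SAP carries out the endpoint as written, with criteria that the protocol describes as the sponsor's predefined set. Placebo is counted by the same rule. Every visit is listed for a subject with a MAV, so the pre-dose value stands beside the post-dose value, and with about 20 subjects separation by hand is feasible. Change-from-baseline summaries and the ECG interpretation shift table are also planned. Table layouts are not in the documents, so heart-rate and RR MAVs may already be reported by parameter.

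Most of this stands. The information exists; what is missing is a planned table that gives the split by treatment. That the criteria are predefined explains where they come from but does not make two cut-offs for one quantity agree.

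Stronger readings are tempting and are not supported:
- A reader might infer that the ECG percentage cannot be computed, or that one row is a mistake. It can be computed, and the documents do not show which pair is intended or whether the difference is deliberate.
- A reader might put a size on the rate mismatch by assuming a heart-rate distribution. A normal distribution with mean 75 to 85 bpm and SD 10 to 15 bpm, one ECG each, gives 0.1 to 2.4 more of 16 subjects flagged by either row than by the heart-rate row. The mean and SD are assumptions. The comparison also leaves out PR, QRS, QT and QTcF, through which the same subject may already be counted, so it does not measure the effect on the any-ECG percentage.

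**Conclusion.** Both parts hold. The disagreement between the rows is exact arithmetic: 20 bpm at the fast end and 8.3 bpm at the slow end, in opposite directions. The MAV percentages mix new and pre-existing abnormalities by construction, except in one QTcF branch, and no planned table separates them by treatment.

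The effect on the reported counts is unknown, because the documents give neither a heart-rate distribution nor baseline MAV frequencies. The figures of 6.25 and 25 points are upper bounds per subject at the planned arm sizes, reached only when that subject is not already counted for another reason.

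A reader might infer that the percentages are biased against TAK-935 or that a test is affected. Neither follows: the same rule applies to both arms, and no test or decision rule uses these counts. The loss is in the interpretation of a named secondary safety endpoint. That justifies a correction but does not threaten the trial.

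**What to change.** **Appendix C.** The sponsor should make the heart-rate and RR rows equivalent, or state that the difference is intended and report the two kinds of MAV separately. Since the intended pair is not known, neither row should simply be deleted.

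**Tables.** Keep the planned any-post-dose count. Add, by parameter and treatment, either a treatment-emergent count (criterion not met at baseline) or a baseline-by-post-dose MAV table. For subjects already beyond a limit at baseline, show the baseline and worst post-dose values so that worsening stays visible.

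**Reference value.**
- Part 1: the Part 1 baseline.
- Part 2: count Part 2 values only, but judge whether a MAV is new against the last value before the first TAK-935 dose. Baseline II in SAP Table 7.b is an on-drug value for subjects given TAK-935 in Part 1. SAP 7.1.1 also describes the Part 2 baseline once without naming the part, so the reference should be stated explicitly and labelled apart from the baseline of the change tables.
- Combined: count all values after the first TAK-935 dose against that same value.

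**Cost.** One clarification and one small table per domain for Part 1, Part 2 and combined: 3 × 3, so up to nine tables, all from data already collected. Many cells will be 0 or 1. If the ECG limits change, the ECG percentage becomes slightly less comparable with other studies that use the sponsor's criteria.
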